### 7.3 CLINICAL LABORATORY ASSESSMENTS

Data for clinical labs will be collected at screening, Day 28 (no prothrombin time (PT) or International Normalized Ratio (INR)), Months 6, 12, 18 and 24. Hematology and clinical chemistry, urine or serum pregnancy test and coagulation (PT or INR) samples will be analyzed at the study site's local laboratory. PRA samples will be collected during screening, Months 6, 12, 18 and 24 and early termination visits (for subjects who discontinue before Month 24 visit) and analyzed at a central laboratory.

Descriptive statistics by time of assessment will be presented for each laboratory parameter. Changes from baseline as well as shift tables will be presented. All laboratory values will be classified as low, normal, or high based on normal ranges supplied by each local laboratory. For purposes of analyses, laboratory results based upon standardized units will be used. Unscheduled visits and repeat measurements will be excluded from table summaries but will be included in data listings.

For each summary, the number of non-missing observations, mean, median, standard deviation, inter-quartile range, minimum, and maximum values will be presented by treatment. Individual clinical laboratory values (clinical chemistry, hematology, and urine or serum pregnancy test, coagulation) will be presented in subject data listings.

See the protocol for details on Laboratory testing on Clinical Chemistry, Hematology, Urine or Serum Pregnancy Test, Coagulation and PRA.

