2.5 Potential Risks and Benefits

2.5.1 Potential Risks

It is anticipated that subjects participating in the study will be exposed to the same risks as those associated with AV graft implantation (some of which have been reported in Phase 2 trial with the HAV – see Investigator Brochure). Risks associated with the HAV and the ePTFE graft may include, but are not limited to, the following:

- Aneurysm or pseudo-aneurysm formation
- Conduit rupture
- Bleeding and hematoma formation at the surgical site or the dialysis puncture sites
- Thrombosis/occlusion of the conduit or host vessels
- Stenosis of the conduit or its anastomoses
- Infection of the conduit, at the surgical site or a systemic infection
- Skin erosion
- Steal syndrome and/or high output cardiac failure
- Swelling of the limb

The risks anticipated in this study are similar to those associated with currently marketed prosthetic grafts used for dialysis access. There was one aneurysmal dilatation of the HAV reported in the Phase 2 experience. The superficial site of implantation of the conduit facilitates clinical and regular ultrasound monitoring, allowing any such complication to be recognized and treated promptly, and thus minimizing potential risk to the subject.

The HAV is grown using donor human aortic smooth muscle cells. The HAV is decellularized during manufacturing and thus consists of only human ECM proteins. It is possible that the HAV may provoke an immune response which may lead to damage of the HAV and possible cross reactivity against host proteins. Antibody formation will be assessed by monitoring of PRA levels.

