8.5.1.8 Assessment of Adverse Events

The subject will be asked general questions about his/her health and for any conduit or dialysis problems since the previous visit. See [Section 9](#) for information regarding AE collection and data handling.

8.5.2 Evaluations and Procedures to be performed only at Specific Visits from Month 2 to Month 24

8.5.2.1 Duplex Ultrasound: Month 2, 3, 6, 12, 18 and 24

A duplex ultrasound will be performed to assess study conduit patency, diameter of the lumen mid-conduit, implant and anastomotic stenosis, volumetric flow rate, and to monitor for aneurysm development. The full length of the study conduit should be visualized with particular attention paid to any increase in diameter of the conduit that might indicate aneurysm formation.

8.5.2.2 Document Removal of CVC that was in place Pre-randomization: Month 2 and 3

Record the date and reason for removal of the CVC that was in place pre-randomization, if applicable.

8.5.2.3 Additional Data from Dialysis Unit: Month 3, 6, 12, 18 and 24

For a subset of subjects, the CRO will obtain, via data transfers from dialysis organizations, the following data obtained at a time closest but prior to the study visit (these data will be obtained from labs drawn at the discretion of the dialysis unit; where feasible and appropriate, these data will be obtained prior to study conduit implantation, too):

- $\text{spKt}/V_{\text{urea}}$ (to enable assessment of dialysis efficiency)
- Hemoglobin
- Erythropoiesis-stimulating agent (ESA) used and dose
- HbA1c (last value prior to study conduit implantation only)

8.5.2.4 PRA: Month 6, 12, 18 and 24

PRA samples will be drawn at Month 6, 12, 18, and 24. PRA samples should also be drawn prior to transplantation for any subjects who receive a transplant during the study.

8.5.2.5 Laboratory Data: Month 6, 12, 18 and 24

At Month 6, 12, 18 and 24, a blood sample will be collected for the following:

- Hematology: hemoglobin, hematocrit, RBC, WBC with differential, platelet count.
- Clinical chemistry: sodium, potassium, calcium, BUN or urea, creatinine, albumin, total bilirubin, ALT, AST, alkaline phosphatase, glucose (non-fasting)

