9. SAFETY ASSESSMENTS AND ADVERSE EVENTS

The safety of the HAV and the ePTFE graft will be assessed in terms of the following:

- Anastomotic bleeding or spontaneous rupture
- Conduit dilatation (aneurysm formation [conduit lumen diameter >9 mm] or pseudo-aneurysm)
- Conduit spontaneous rupture
- Conduit infection
- Need for conduit removal
- Access-related bleeding requiring intervention
- Other AEs
- Laboratory parameters (clinical chemistry and hematology)
- Increase from baseline in PRA

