| 5.0
08AUG2018               | 6.1                  | Added subject withdrawal due to non-compliance to the censoring rule.

Added hazard ratio margin calculation.  | Updated for clarifications  |
| 5.0
08AUG2018               | 6.2                  | Deleted analysis for number of interventions needed to maintain patency prior to loss of primary assisted patency.   | Removed to reflect planned analysis for the study.                        |
| 5.0
08AUG2018               | 6.3                  | Added subject withdrawal due to non-compliance to the censoring rule.  | Updated for clarifications  |
| 5.0
08AUG2018               | 7.2, 7.2.2,
7.2.4 | Added the statement for imputing an AE start date if it was partially missing.

Added the analysis for Sponsor assessed AE relationship to IMP and study procedure(s).                           | Updated for clarifications and to reflect planned analysis for the study. |
| 5.0
08AUG2018               | 7.2.5                | Removed the analysis for the relationship of the infection to the presence of access for dialysis other than study conduit.  | Removed to reflect planned analysis for the study.                        |

| Protocol Version # | SAP Section | Modification  | Description and Rationale  |
|---------------------------|--------------------|--|---|
| 5.0
08AUG2018          | 7.2.6              | Modified the language for aneurysms and pseudo-aneurysms analysis.

Added analysis for thrombosis, stenosis and bleeding of study access | Updated for clarifications and to reflect planned analysis for the study. |
| 5.0
08AUG2018          | 7.3                | Removed PRA from the analysis  | Removed to reflect planned analysis for the study.                        |
| 5.0
08AUG2018          | 9                  | Added “if applicable” at the end of the sentence.  | Updated for clarifications.   |

The table below details the changes made to the SAP version 5.0 (01May2019) to reflect the planned analysis for Month 24.

| Protocol Version # | SAP Section | Modification  | Description and Rationale  |
|---------------------------|--------------------|--|---|
| 5.0
08AUG2018          | 6.1                | Removed withdrawal due to non-compliance.

Updated the language for non-inferiority hazard ratio margin calculation. | Updated for clarifications and to reflect planned analysis for the study. |

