## **7 SAFETY ANALYSIS**

Safety assessments will include clinical chemistry, hematology, coagulation (prothrombin time or International Normalized Ratio (INR)), PRA, vital signs, adverse events, symptom directed physical exams and Duplex ultrasound assessments. Summaries of all safety assessments will be reported by visits where data are collected.

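### The SAP conflicts with itself on whether PRA, the protocol's monitor for an immune response to the HAV, will be reported

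*SAP*

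**What the plan says.** **Protocol.** Section 2.5.1 states the risk, with host proteins as the target of any cross reaction: "It is possible that the HAV may provoke an immune response which may lead to damage of the HAV and possible cross reactivity". It then names the monitor: "Antibody formation will be assessed by monitoring of PRA levels". Section 9 includes "Increase from baseline in PRA" in its list of how the safety of both conduits will be judged. Section 10.4 tests access-related infection and says that the remaining safety data are described without inference. On sampling, 8.1.7 takes a PRA sample at Screening, and 8.5.2.4 adds "PRA samples will be drawn at Month 6, 12, 18, and 24" and, for the pre-transplant draw, "PRA samples should also be drawn prior to transplantation for any subjects who receive a transplant during the study". Section 8.7.9 adds a sample at early termination before Month 24.

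**SAP.** Section 7 names PRA among the safety assessments and adds: "Summaries of all safety assessments will be reported by visits where data are collected". Section 7.3 repeats the PRA collection times and says a central laboratory will test the samples. It then gives general rules for laboratory data: descriptive statistics for every parameter, changes from baseline, shift tables, and classification against the local laboratories' normal ranges. Its listing sentence reads: "Individual clinical laboratory values (clinical chemistry, hematology, and urine or serum pregnancy test, coagulation) will be presented in subject data listings". The log of changes made to SAP version 4.0 has, against Section 7.3, the entry "Removed PRA from the analysis", with the reason that this reflects the planned analysis.

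**The concern.** PRA is the only measurement that the protocol assigns to antibody formation against a product grown from human donor cells. The protocol commits to collecting it in both arms and to describing it. The SAP leaves open whether that description will be produced, and its laboratory section leans towards leaving it out.

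What is at stake is a by-arm description of change in PRA, with the ePTFE arm as a concurrent randomised control. If the laboratory section is followed as its revision intends, subjects will have given blood for a stated safety purpose and the planned outputs will not show the result.

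**Working it through.** No power, alpha or margin is involved, and the documents state no rate or threshold for PRA. The check sets the passages side by side.

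1. **What was promised.** Protocol 2.5.1 makes PRA the monitor, Protocol 9 lists an increase from baseline as a safety assessment, and Protocol 10.4 says safety data other than infections are described. Together these commit to a description of PRA by arm, and to no test.

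2. **How much is collected.** Scheduled samples are Screening plus Months 6, 12, 18 and 24, which is 5 per subject. With the planned 350 implanted subjects, 5 × 350 = 1,750 scheduled samples if everyone attends every visit, and fewer with dropout. Early-termination and pre-transplant draws come on top. This is the scale of collection, not a count of results shown to go unreported.

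3. **What each part of the current SAP implies for PRA.**
   - Section 7: PRA is in, summarised by visit.
   - Section 7.3, descriptive statistics and change from baseline: PRA is neither named nor excluded. The general wording could cover it.
   - Section 7.3, classification: cannot be applied to PRA as written, because the ranges come from local laboratories and PRA is run centrally.
   - Section 7.3, listings: four categories are named and PRA is not one of them. The closing sentence of the same section, which refers the reader to the protocol for testing details, names those four and PRA. The shorter list therefore looks intended.
   - Section 4, listing of all case report form data: covers PRA only if the central results enter the case report form. Neither document says so. Protocol 8.8.1 has the PRA vials shipped to the sponsor.
   - No section defines an increase in PRA. Section 4.6 gives only the general definition of baseline.

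4. **What follows.** A programmer working from Section 7 would produce PRA tables. One working from 7.3 could leave PRA out. Each could cite the SAP.

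5. **What the log adds.** The conflict stands in the current text without the log. The log is evidence only of which reading was intended, and it favours omission. Its stated reason restates the decision. The entry cites protocol version 5.0, the version in which 2.5.1 and 9 still carry PRA, so no change to the protocol accompanies the removal.

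**The case against.** The strongest reply is that PRA is still covered. Section 7 names it, 7.3 promises statistics for every laboratory parameter, Section 4 lists all case report form data, and Protocol 12 calls for a study report summarising all available data. Section 4 also lets lesser changes to protocol-described methods be justified in the study report. PRA is not an endpoint in Protocol 4.2, and damage to the conduit would also show in patency, aneurysm, rupture and histology.

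Part of this stands. The coverage argument rules out saying that PRA will go unreported. It does not remove the conflict, because the section written for laboratory data omits PRA and the log says the omission was meant. A justification in the study report would come too late to settle the outputs. The other outcomes show conduit damage, whereas the protocol gives antibody formation to PRA alone. That PRA is not an endpoint limits the weight of the point.

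A reader might infer several stronger things that the documents do not support.
- **That PRA was dropped because of what it showed.** With a start in 2Q2016 and 16 months of enrolment, the last implants fall around August to October 2017. Most draws would then predate the removal, which came after version 4.0 of 26 November 2018. But nothing says that anyone had seen PRA results.
- **That a formal comparison with ePTFE was lost.** Only description was promised.
- **That the rule on unscheduled visits discards the pre-transplant sample.** The rule keeps such values in listings and does not touch the scheduled draws. No text classes the pre-transplant draw as unscheduled.
- **That Protocol 8.5.2.4 and Appendix 1 footnote 6 disagree on the pre-transplant draw.** The footnote's limit of Month 24 matches the Month 2 to Month 24 heading above 8.5.2.4.

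**Conclusion.** The point holds as an unresolved conflict over reporting. The protocol assigns PRA to a named risk and lists its increase as a safety assessment. SAP Section 7 promises to summarise it, while SAP 7.3 leaves it out of the listings, applies a classification that does not fit it, and was revised with the stated aim of removing it, without a scientific reason. If 7.3 is followed as revised, one protocol-listed safety assessment, collected in both randomised arms, would not be described. This conclusion rests on reading 7.3 as the controlling section for laboratory outputs, and on central PRA results not reaching the listings through the case report form; the documents settle neither. The primary and key secondary efficacy analyses are unaffected. The change should be made because the commitment is explicit and the cost is small.

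**What to change.** Restore PRA by name in SAP 7.3:

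- A descriptive table by arm and scheduled visit, with level and change from baseline, and with early-termination values shown.
- A definition of an increase, written down before PRA is analysed by arm. The local-laboratory classification should be stated not to apply to PRA.
- PRA added to the subject listings, including any pre-transplant draws.

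Section 7 can then stand as it is. No inferential test is needed, and Appendix 1 footnote 6 need not change. A summary of each subject's highest value from any sample should be avoided, because it depends on how many samples a subject has, and that number may differ between arms with follow-up, early termination or transplant.

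The cost is one table and one listing from samples already collected, with no new procedure or subject.

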## **7.4 VITAL SIGNS**

All vital sign measurements including temperature will be summarized by treatment group using descriptive statistics (n, mean, median, standard deviation, minimum and maximum). A listing of vital signs will also be reported.

## **7.5 PHYSICAL EXAMINATION**

The number and percentage of subjects with relevant physical examination abnormalities at Screening will be summarized and presented for each body system. A listing of abnormalities will also be provided.

## **7.6 SUBJECT AND GRAFT STATUS**

Summaries of subject status (alive or deceased), study conduit patency/usability, evidence of clinically significant aneurysm formation of the study conduit by clinical examination, need for interventions to maintain or restore patency of the study conduit and reasons for study conduit abandonment will be reported by frequency counts and percentages. Listings of the subject and graft status including the parameters provided above will be provided.

## **8 OTHER MEASURES**

Summaries will be presented for Duplex ultrasound, dialysis and placement of a central venous catheter, time to first cannulation, clinical examination of conduit and interventions, surgical placement of conduit and documentation of any complications. All data indicated in this section, as well as vessel mapping data, will be listed.

## **9 CLINICAL EVENTS COMMITTEE ANALYSIS**

Results from CEC assessment of compliances, CEC adjudication of study conduit revisions, and CEC adjudication of access-related infections will be summarized by country and by site if applicable.

## **10 INTERIM ANALYSIS**

Not Applicable.

## 11 SAMPLE SIZE AND POWER CALCULATIONS

The original sample size calculation was based on the following assumptions:

For the primary endpoint of time to loss of Secondary Patency, the assumed 12-month event-free rates in the ePTFE graft is 60%. Based on 1:1 randomization, a 16-month enrollment period, and a 12-month follow-up period, a total sample size of 350 subjects will provide greater

- 90% power to demonstrate non-inferiority (with a 10% non-inferiority margin) if the 12-month event-free rate in the HAV arm is 66%
- 90% power to demonstrate superiority if the 12-month event-free rate in the HAV arm is 76%

For the key secondary endpoint of time to loss of Primary Patency, the assumed 6-month event-free rate in the ePTFE graft arm is 50%. Based on 1:1 randomization, a 16-month enrollment period, and a 12-month follow-up period, and under the assumption that the true 6-month event-free rate in the HAV arm is 55%, a total sample size of 350 subjects will provide greater than 90% power to demonstrate non-inferiority (assuming a non-inferiority margin of 10%). If the true rate in the HAV arm is as low as 53%, then there will be greater than 80% power to demonstrate non-inferiority.

During the course of the study a high enrolling site (~10% of total subjects) early terminated all of their remaining subjects and withdrew from study participation. The majority of these subjects had not yet had an event that would contribute to the primary endpoint analysis. To mitigate the potential loss of study power from this unexpected situation, the decision was made to extend the follow-up period for the primary and secondary efficacy analyses from 12 months post-implant to 18 months post-implant.

## **13 APPENDICES**

### **13.1 APPENDIX A: SCHEDULE OF STUDY PROCEDURES**

See Study Protocol Appendix 1, pages 94 through 96 for details.

